## H.2.b. Endpoints

**Primary:** Difference in the change in HbA1c from baseline to 24 weeks (+/-2 weeks) post-discharge (%, mmol/l)

**Secondary:**

- Difference in the change in HbA1c from baseline to 12 weeks (+/-2 weeks) post-discharge (%, mmol/l)
- Difference in the change in HbA1c from baseline to 12 and 24 weeks (+/-2 weeks) post-discharge (%, mmol/l)
- Difference in the change in fasting plasma glucose (FPG) from baseline to 12 and 24 weeks in DOS vs ESC (mg/dl)
- Difference in the % of patients achieving HbA1C 7% in DOS vs ESC (12, 24 weeks)
- Difference in the % of patients achieving HbA1C 6.5% in DOS vs ESC (12, 24 weeks)
- Difference in the % of patients achieving individualized HbA1C target in DOS vs ESC (12, 24 weeks)
- Difference in the proportion of patients with accurate and complete discharge orders for basal insulin and related supplies. (%)
  - Assessed as complete dose, quantity dispensed, adequate refills (separate for basal and prandial insulin), and correct prescription for pen needles (presence, quantity, adequate refills), no jargon
- Difference in the proportion of patients with accurate and complete discharge orders for prandial insulin and related supplies. (%)
  - Assessed as complete dose, clear dosing instructions, quantity dispensed, adequate refills, and correct prescription for pen needles (presence, quantity, adequate refills), no jargon
- Difference in the proportion of patients with a discharge prescription for glucose monitoring supplies (%)
- Difference in adherence to glargine U300 (% taking >80% of doses) at 2, and 24 weeks
- Difference in the proportion of patients who remain on glargine U300 at 24 weeks (%)
- Difference in the mean dose of glargine U300 at 2 and 24 weeks (units)
- Difference in the frequency of glucose monitoring at 2 and 24 weeks (times per day)
- Difference in the proportion of patients who follow up with their primary care provider or endocrinologist within 2, 6 weeks of discharge (%)
- Difference in the incidence of documented symptomatic (BG <54 mg/dl) hypoglycemia (%)

**H.2.c Primary Aim: To determine whether a Discharge order set with nursing support (DOS) is associated with lower HbA1c at 24 weeks post-program than enhanced standard care (ESC) alone.** We will test for a difference in 24 week change in HbA1c between the DOS and ESC groups using a linear mixed model for the longitudinal HbA1c measurements. Our model will contain a random subject-specific effect and fixed effects of time (baseline vs. 24 weeks), treatment, a treatment-by-time interaction, and baseline covariates related to change, which we expect to include age, whether or not patient is new to insulin, and dose of insulin based on our preliminary data. We will adjust for changes in prandial insulin dose by including dose as a time-varying covariate in our mixed models. The inclusion of covariates is not to account for differences in these factors across treatment groups (which we don't expect due to randomization) but to increase the precision of our treatment effect estimate. A Wald test of the treatment-by-time interaction will be used to test our primary hypothesis that DOS affects 24 weeks change in Hb1Ac.

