### **Insulin Titration in the era of Longer-acting Basal insulins**

Previous studies indicate that patients beginning either basal or prandial insulin achieve the greatest benefit from inpatient education following hospital discharge. These patients often undergo optimization of the insulin dose prior to discharge. Most previous inpatient studies have utilized daily titration algorithms. Insulin stacking has not been a significant concern, since higher treatment targets are generally implemented and only small adjustments (10-20%) in the total daily dose are made. In contrast, daily titration may not be appropriate for newer longer-acting insulins, even at higher treatment targets. For example, glargine U300 (Toujeo) is a concentrated formulation of glargine with a longer duration of action than glargine U100 (Lantus). Therefore, titration is not recommended more frequently than every 3-4 days. In addition, patients receiving glargine U100 in the hospital who are transitioned to glargine U300 at discharge will require approximately 11 - 17.5% more insulin to maintain equivalent glycemic control. This is further complicated by changing insulin requirements in the setting of resolution of illness and glucotoxicity as well as changes in diet and activity following discharge. As a result, additional titration will be necessary following discharge for many patients. Finally, while numerous studies support patient self-titration of insulin, these studies are generally conducted among highly motivated ambulatory patients. It is unclear whether patient self-titration is feasible in recently hospitalized patients.

Glargine U300 (300 units/mL) is 3-fold more concentrated than traditional insulin glargine U100. It has a smaller depot surface area, thereby reducing the rate of absorption. As a result, glargine U300 provides flatter and more prolonged pharmacokinetic and pharmacodynamic profiles compared to standard insulin glargine. Its duration of action is  $\leq$ 36 hours, and its half-life is approximately 23 hours.

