#### **D.2.g. Program Completion**

Participants will receive an order to complete the HbA1c at 12 and 24 weeks at any OSU lab. A reminder letter will be sent 1 week prior to the date and a phone call reminder will occur 2 days before the visit. Study team will complete the 12 week and 24 week call and search the electronic medical record and primary provider's chart for HbA1c and healthcare utilization at 12 and 24 weeks.

**E. Study Drug:** Patients in both groups will be provided standard of care insulin therapy throughout the study, including insulin glargine (TOUJEO® U300) plus additional background therapy (non-insulin and prandial insulin therapies), based upon discharge team preference. The starting dose will be determined during hospitalization from the dose of glargine/detemir U100 in a 1:1 dose conversion. Upon discharge, standard titration instructions (every 4 days) will be implemented in the DOS group but will be left to the discretion of the discharge team in the ESC group.

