#### H.1.a. Missing Data

All data analyses will be completed as intention to treat analyses (i.e., individuals analyzed by group according to original random assignment, without regard to adherence to the intervention).

Longitudinal outcomes (e.g., HbA1c) will be analyzed using mixed models utilizing all available measurements from individuals randomized. Missing binary outcomes (e.g., accurate and complete discharge orders, adherence) and missing covariate data will be imputed, using multiple imputation in SAS v9.3 PROC MI.

Table 9. Study Procedures and Visits

Visit number	0	1	2	3	4
Time of Visit	Screen/consent	2 week	6 week	12 week	24 week
Type of visit	In-person	Phone	Phone	In-person	In-person
Informed consent/contact team	x				
Randomization	x				
Load DOS into EMR and inform discharge team	x				
Provide study drug and glucose monitoring instructions	x				
Demographics/Socioeconomic status	x				
Diabetes history	x				
Hospitalization history	x				
PSS scale	x				
DES-SF	x			x	x
Newest Vital Sign	x				
Glucose/insulin diary	x				
Review DOS		x			
Ascertain health care utilization		x	x	x	x
Review glucose/insulin diary		x	x	x	x
Hypoglycemia/Hyperglycemia		x	x	x	x
Review insulin adherence, persistence		x	x	x	x
Nurse counsellor (DOS group only)		x	x	x	x
HbA1c	x			x	x
Fasting blood glucose	x			x	x

DOS=discharge order set, EMR=electronic medical record, PSS=Perceived Social Support scale, DES-SF=Diabetes empowerment scale-short form, In-Person clinic visits will be conducted at either CarPoint East or McCampbell Hall

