Based upon preliminary data, we found that approximately 30% were of African American race. We are enrolling a wide age range, 25-75, in order to achieve optimal external validity, but have excluded the younger and older participants due to insufficient numbers in those ranges and possibly different educational needs, that may involve people (family) other than the patient. Participants are anticipated to be sick and have other comorbidities (in our pilot data, 70% were admitted for a problem that was not directly related to diabetes). However, all participants will be free-living in the community and have a phone. Due to bias introduced by additional support staff at institutions such as nursing homes and rehabilitation centers, these participants will be excluded. Participants who are unable to provide consent in English will be excluded as this number is very small and will hinder motivational interviewing (MI) process. Other vulnerable populations, such as prisoners will be excluded. Pregnant individuals will be excluded since the HbA1c is not as reliable and because such individuals have different motivations and follow-up already in place.

Permission will be obtained from the attending physician of the admitting inpatient service prior to approaching participants for enrollment. Randomization will be conducted using a computerized random number generator program that is weighted and will be stratified by race. The frequency of telephone follow-up is felt to be adequate to establish reasonable endpoints for reinforcement of behavior and capture a realistic window for readmission.

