##### A.1.b. *Sources of Materials*

- Blood work will be collected for HbA1c at baseline and follow-up.

- Data that will be collected for both groups include:
  - Contact information, including email address and best times to reach the patient, contact information for two emergency contacts, and contact information of the patient's primary care provider
  - Type of diabetes, complications, duration
  - Education level, marital status, work status, home ownership, medical coverage, and demographics
  - Social support, measured using the Multidimensional Scale of Perceived Social Support.
  - Reason for hospital admission, medical history, concomitant medications, weight, height, BMI, standard of care lab results
  - Functional health literacy assessment.
  - Diabetes Empowerment Scale Short-Form (DES-SF): The DES-SF will be obtained at baseline and follow-up
  - Charlson comorbidity index
  - Blood Sugar Log
  - Outcomes including readmission or other acute care services, outpatient physician follow-up, medication adherence. Records will be requested from outpatient providers as needed.

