### **A.2 Adequacy of Protection Against Risks**

#### *A.2.a Recruitment and Informed Consent*

Potential participants will be identified during their hospitalization through screening inpatient medicine and surgery wards. A partial HIPAA waiver will be obtained for this purpose. Permission will be obtained from the admitting team's attending physician or appropriate designee. The patient will be approached in private. Personnel (coordinator) will describe the purpose of the study in the same words that are used on the consent form, which states lack of participation will not otherwise influence patient care. Participants are expected to read the consent form (or have it read to them) in full and be able to explain the study purpose, risks, and procedures to the investigator before consent will be considered complete and informed. Participants will be encouraged to ask questions and have any questions answered to their satisfaction. Participants that seem unsure or want to consider it further will be re-approached with their permission, after several hours or the following day or otherwise per the participant's request. The samples and study-related information will not be used if the participant subsequently declines enrollment.

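### Fasting glucose is defined as change from an in-hospital baseline and has no named model; using that baseline as a covariate would make the arm comparison at least as precise

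*Combined protocol and SAP*

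**What the plan says.** **Endpoint.** Section H.2.b, Secondary: "Difference in the change in fasting plasma glucose (FPG) from baseline to 12 and 24 weeks in DOS vs ESC (mg/dl". The synopsis has the same endpoint in shorter form.

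**Timing.** Table 9 (under H.1.a) has a row "Fasting blood glucose" marked at visit 0 (screening and consent), week 12 and week 24. Visit 0 is an inpatient visit: "Potential participants will be identified during their hospitalization through screening inpatient medicine and surgery wards" (Human Subjects, A.2.a). No section gives the hospital day, or the stage of insulin adjustment, at which the baseline sample is drawn.

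**Patient state at baseline.** The background section on insulin titration says "These patients often undergo optimization of the insulin dose prior to discharge", and then refers to "changing insulin requirements in the setting of resolution of illness and glucotoxicity as well as changes in diet and activity following discharge". Human Subjects A.1.a reports that in the pilot "70% were admitted for a problem that was not directly related to diabetes".

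**Analysis.** H.1.a assigns longitudinal outcomes to mixed models, with HbA1c as the example. H.2.c gives the HbA1c model: baseline is one level of time, and the test is the treatment-by-time interaction. H.2.d gives a method for binary outcomes only. Fasting glucose is named in none of the three.

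**Collection.** D.2.g: "Participants will receive an order to complete the HbA1c at 12 and 24 weeks at any OSU lab". Human Subjects A.1.b: "Blood work will be collected for HbA1c at baseline and follow-up". The reminder letter and call in D.2.g do not mention fasting.

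**The concern.** HbA1c reflects control over the preceding weeks, so an inpatient HbA1c still describes the patient's state before admission. A single inpatient fasting glucose describes a morning under hospital diet, hospital-managed insulin and often acute illness. On the plan's own account those conditions change after discharge. If the value predicts later fasting glucose only weakly, subtracting it adds noise to each patient's outcome and removes little between-patient variation.

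What is at stake is precision. Fasting glucose is the laboratory outcome close to the target that basal titration aims at, and H.2.a plans no power for it. Avoidable variance is therefore not covered by any margin in the sample size.

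**Working it through.** **1. The plan's own figure.** H.2.a gives, for HbA1c, n per group = 4σ²(1−ρ)(1−R²)(z₀.₉₇₅+z₀.₈₀)²/Δ², with σ = 2.2, ρ = 0.25, R² = 0.5 and Δ = 0.8. This is 4 × 4.84 × 0.75 × 0.5 × 7.849 / 0.64 = 89.04, against 89 stated. Then 89/0.8 = 111.25, against 111 stated. Both reproduce. The factor 2σ²(1−ρ) inside the formula is the variance of a change score. No SD, correlation or sample size is given for fasting glucose.

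**2. Variance of the arm comparison, equal SDs.** Take a comparison of follow-up values alone as 1. A change score has 2(1−ρ), and baseline adjustment (ANCOVA) has 1−ρ². The ratio is 2(1−ρ)/(1−ρ²) = 2/(1+ρ). The correlation is an assumption, so a range is shown. Detectable differences are in SD units at 80% power, two-sided 0.05, with 89 per arm: 2.80 × √(2v/89), where v is the variance in the table.

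| ρ (assumed) | Change score | Adjusted | Ratio | Change-score power where adjusted has 80% | Detectable difference, change vs adjusted |
|---|---|---|---|---|---|
| 0 | 2.00 | 1.00 | 2.00 | 51% | 0.59 vs 0.42 |
| 0.25 | 1.50 | 0.9375 | 1.60 | 60% | 0.51 vs 0.41 |
| 0.5 | 1.00 | 0.75 | 1.33 | 68% | 0.42 vs 0.36 |
| 0.7 | 0.60 | 0.51 | 1.18 | 73% | 0.33 vs 0.30 |

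**3. Unequal SDs.** Let k = baseline SD / follow-up SD. The change score then has 1+k²−2ρk, and the ratio is (1+k²−2ρk)/(1−ρ²). At ρ = 0.25:

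- k = 0.5: 1.00/0.9375 = 1.07
- k = 1: 1.50/0.9375 = 1.60
- k = 1.5: 2.50/0.9375 = 2.67

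**4. Direction.** The change-score variance minus the adjusted variance is (1+k²−2ρk) − (1−ρ²) = (k−ρ)². This is never negative and is zero only when ρ = k. In large samples, adjustment is therefore at least as precise whatever the unknown values are.

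**5. The primary model carried over.** In one complete simulated data set (ρ = 0.25, 89 per arm), the interaction from a random-intercept model equalled the raw difference in change: −0.1925, SE 0.1695. ANCOVA on the same data had SE 0.1369. Treating baseline as a response level therefore does not avoid the loss.

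**6. Simulation.** With 4,000 runs at 89 per arm, the variance ratios were 2.03, 1.60 and 1.29 at ρ = 0, 0.25 and 0.5 (theory 2.00, 1.60, 1.33). With no true effect, the mean of every estimator was within 0.003 of zero, so none is biased.

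**The case against.** The best case for the plan is that this is an unbiased comparison on one of many secondary endpoints. The study is powered for the primary endpoint only, and fasting glucose does not appear in the detailed secondary aims in D.1.b and H.2.d. That is correct, and it limits the weight of the point.

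Several stronger readings are tempting, and the documents do not support them:

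- **That the inpatient value is unrelated to control at home.** That would mean ρ = 0. The only correlation given, 0.25, is for HbA1c. The remark on dose optimisation follows a sentence about patients starting insulin in earlier studies, whereas this trial also takes established insulin users (D.2.d stratifies on it). A low correlation is plausible but not shown.
- **That a fixed share of the sample is wasted.** A figure of 37.5% (1 − 1/1.60) needs both ρ = 0.25 and equal SDs. If hospital management narrows the baseline spread to k = 0.5, the ratio at that correlation is only 1.07.
- **That fasting glucose will be analysed as a raw change score.** The endpoint is defined as change, but no model is stated. That the H.2.c model would be used is an inference.
- **That subtracting baseline is worse than ignoring it.** This holds only for ρ below k/2, which is 0.5 with equal SDs.
- **That the change within each arm would mislead.** The endpoint is a difference between arms, and change within an arm is not an endpoint.
- **That follow-up fasting samples are not planned.** Table 9 schedules them at both visits. What stands is that D.2.g and A.1.b name HbA1c only and that the reminders do not mention fasting.

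**Conclusion.** The point holds as one of precision and specification. Fasting glucose is defined as change from a value taken in hospital, and its model is not named. Both natural readings of the plan (a raw change score, or the H.2.c interaction model) give a less precise arm comparison than baseline adjustment, except in the special case ρ = k.

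The size of the loss cannot be fixed from the documents. With equal SDs the variance ratio runs from 2.00 to 1.18 over assumed correlations of 0 to 0.7. At ρ = 0.25 it runs from 1.07 to 2.67 over assumed SD ratios of 0.5 to 1.5. The direction rests on no assumed value of ρ or k, only on randomisation and a reasonably large sample.

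A reader should not infer bias, a threat to the primary analysis or an effect on the sample size. The mismatch between Table 9 and the collection text is a minor, separate alignment.

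**What to change.** 1. **Analysis.** Define the endpoint as the between-arm difference in fasting glucose at 12 and at 24 weeks, with baseline fasting glucose as a covariate. Use ANCOVA at each visit, or a mixed model over all three visits with a common baseline mean for the two arms. In the mixed model, let variances and correlations differ by visit, so that the adjustment is not tied to equal SDs. Baseline HbA1c may be added as a further covariate. Name the chosen model in section H.2.
2. **Baseline timing.** State when in the admission the baseline fasting sample is drawn, and that it precedes randomisation.
3. **Alignment with Table 9.** Name fasting glucose in the D.2.g lab order and in Human Subjects A.1.b. Add a fasting instruction to the existing reminder letter and call, and record whether each sample was confirmed as fasting.

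The cost is a few lines of text. Table 9 already schedules the measurement at all three visits, and no extra patients are needed. The small downside is that patients must attend the 12- and 24-week visits fasting.

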### C.2.c. Study 3: Clarity and effectiveness of EMR based discharge procedures in patients with stress hyperglycemia: role of the diabetes consult service

Patients without prior diagnosis of diabetes (HbA1c <6.5% without pre-admission glucose lowering therapy) who were discharged on any anti-diabetic medication following cardiac surgery were identified and individual chart reviews were performed. Outcomes of interest included discharge and follow-up medications as well as clarity of discharge instructions, stratified by electronic medical record (EMR) and diabetes consult service (DCS) status.

A total of 125 patients were identified (Table 5). Patients had a baseline HbA1c of 5.8 +/- 0.41% and admission (random) glucose of 7.6 +/- 2.3 mmol/L. At discharge, 76, 31, and 33% of patients received oral agents, bolus insulin, or basal insulin respectively. EMR discharge instructions were clear in 67% of patients overall, including 83, 54, and 20% of patients receiving oral agents, basal insulin and bolus insulin respectively. At the 6 week post-operative follow-up visit, 44, 9 and 6% still had these respective therapies listed. DCS involvement was less frequent following conversion to an inpatient EMR but was associated with better glucose control (similar admission glucose but lower peak and a trend for higher trough glucose levels). Patients with diabetes consults were more frequently discharged on oral agents as opposed to insulin, and had greater frequency of clear discharge instructions (Table 5). The most common reason for unclear discharge instructions was medical jargon prior to the EMR, while it was conflicting instructions (either with the consult notes or within the prescription itself, typically because insulin regimens require “free text” rather than direct entry of dosing fields, Figure 1).

**Conclusion:** The need for glucose lowering therapies at discharge may represent prediabetes or unrecognized type 2 diabetes, but requirements generally decline over time. The data illustrate the extent of unclear EMR based discharge instructions, particularly for patients requiring insulin. A systematic, multidisciplinary team approach may improve processes of care at discharge.

Table 5. Baseline and Hospital Information Stratified by Diabetes Consult Service Involvement

	Overall	No Diabetes Consult (N=19)	Diabetes Consult (N=106)	p-Value
Age (Year)	61+/-13	67+/-14	60+/-12	0.07
Male	93 (74%)	9 (47%)	84 (79%)	0.008

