#### H.2.d. Secondary Aims:

- Determine whether DOS is associated with lower HbA1c at 12 months compared to ESC.
- Determine whether the DOS in conjunction with nurse supported self-titration of basal insulin glargine U300 is associated with improved persistence with insulin therapy, adequate dose titration, and use of self-monitored blood glucose.
- Determine whether the DOS is associated with improved discharge instructions and processes of care for insulin-requiring patients. This will be measured in terms of clarity of instructions, adequacy and completeness of prescriptions for insulin and diabetes supplies, and follow-up plan.

Each of these secondary outcomes will be binary (e.g., adequate vs. inadequate dose titration). Missing values of the outcomes will be imputed using treatment group and baseline covariates. The difference in proportions between treatment groups will be computed for each data set and the results will be combined using Rubin's rules to obtain a final two-sample test of proportions.

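### The basal discharge-order endpoint leaves out the clarity item that its prandial counterpart has, although the secondary aim promises to measure clarity of instructions

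*Combined protocol and SAP*

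**What the plan says.** The secondary aim on discharge processes appears in the synopsis, in D.1.b and in H.2.d: "This will be measured in terms of clarity of instructions, adequacy and completeness of prescriptions for insulin and diabetes supplies, and follow-up plan".

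H.2.b turns this into separate endpoints for basal and prandial orders, each a proportion of patients with accurate and complete orders. The basal criteria are "Assessed as complete dose, quantity dispensed, adequate refills (separate for basal and prandial insulin), and correct prescription for pen needles", with presence, quantity and refills checked for the needles, and then an item requiring no jargon. The prandial criteria are "Assessed as complete dose, clear dosing instructions, quantity dispensed, adequate refills, and correct prescription for pen needles (presence, quantity, adequate refills), no jargon".

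Section E and Table 7 give glargine U300 to both arms at discharge. Prandial insulin is background therapy that depends on the discharge team's preference.

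Study 3 (C.2.c) is the sponsor's evidence on unclear instructions. It reports: "The most common reason for unclear discharge instructions was medical jargon prior to the EMR", and continues "while it was conflicting instructions (either with the consult notes or within the prescription itself". It found basal instructions clear in 54% of patients who received basal insulin. C.2.d says the trial will address the discharge problems seen in these studies, unclear instructions among them.

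**The concern.** The two lists are parallel in every respect but one: the clarity item is in the prandial list and not in the basal list. It is therefore missing from the order that every participant is meant to have.

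Clear basal directions are also a main thing the intervention supplies. F.2.a says the order set is meant to make communication clear as well as complete. F.2.b and the basal menu in the Appendix provide structured dosing and titration wording. The basal endpoint does not score that wording beyond the dose and the absence of jargon. It does score items the order set fills by default: Table 8 and the Appendix pre-set the number of pens, the refills and the linked pen needles.

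Two errors of interpretation follow. A true gain in basal clarity may be diluted because unclear orders pass in both arms. Or a gain in supply items may be reported as better instructions. Section J plans the first manuscript on processes of care at discharge, so this endpoint will carry weight in the trial's reporting.

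**Working it through.** The plan attaches no figure to the order endpoints, so the check is a comparison of texts followed by a scoring exercise.

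**Step 1. The two lists in H.2.b side by side.**

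| Criterion | Basal | Prandial |
|---|---|---|
| Complete dose | yes | yes |
| Clear dosing instructions | **no** | yes |
| Quantity dispensed | yes | yes |
| Adequate refills | yes | yes |
| Pen-needle prescription correct | yes | yes |
| No jargon | yes | yes |
| Conflict named explicitly | no | no |

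The prandial list names both a complete dose and clear instructions. The first is therefore not meant to stand in for the second.

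**Step 2. Score four example orders by the written rules.** Each has a complete dose and correct supplies.

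- Basal, plain language, directions that contradict each other or the consult note: every listed item is met, so it passes.
- Prandial, same defect: Study 3 treats conflict as a reason for instructions being unclear, so on the plan's own usage it fails the clarity item.
- Basal, written in jargon: it fails.
- Basal, clear, with no titration text: it passes, and should. Section E leaves titration in the control arm to the discharge team, and the Appendix menu itself offers an option of no titration.

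Only the first result is at odds with the aim.

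**Step 3. What the gap does to the comparison.** Let p be the share of basal orders in an arm that truly meet the full standard, clarity included. Let m be the share of the remaining orders that the written list still passes. The scored proportion is p + m(1 − p). If m is the same in both arms, the scored difference is

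(p_DOS − p_ESC) × (1 − m).

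The true difference shrinks by the factor 1 − m: to 0.75 of itself at m = 0.25, 0.50 at m = 0.50 and 0.25 at m = 0.75. These values of m are assumptions that show the range; the documents give neither m nor the rate expected with the order set. If m differs between arms, the distortion can go in either direction.

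**Step 4. Can Study 3 supply m?** No, for three reasons.

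- Population: Study 3 covers patients without a prior diabetes diagnosis who were discharged on glucose-lowering drugs after cardiac surgery.
- Period: Table 5 puts 37 of 125 patients after the EMR conversion (37/125 = 29.6%), so 88 of 125 (70.4%) came before it. No basal clarity rate is given for the later period.
- Cause: unclear orders include those unclear through jargon, which the basal list already fails. The split by reason is in Figure 1, which is not reproduced in the text available.

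The 54% also rests on about 41 patients with basal insulin (Table 5), that is, about 0.54 × 41 = 22 with clear instructions.

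**Step 5. Reach.** H.2.a powers the study for the primary endpoint only. The 222 participants and the HbA1c analysis do not depend on this definition.

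**The case against.** The strongest defence is that the endpoint is less lax than it looks. An order does not pass on refills alone: it also needs a complete dose, correct needles and no jargon, and jargon is one of the two main causes of unclear instructions in Study 3. Both endpoints are headed accurate and complete, and a careful abstractor might refuse to call a self-contradicting order accurate. The basal list carries a remark about scoring refills separately for basal and prandial insulin, which suggests it was split from a single combined definition; if so, the missing item is a drafting slip and not a choice. That is an inference.

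What stands: jargon is covered, and the prandial list, read with Study 3, should already fail a conflicting order. For prandial insulin the weakness is an undefined term, not a missing check. A reader might infer from the table above that neither endpoint guards against conflict; for prandial orders the documents do not support that.

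What does not stand: reliance on the word accurate. The listed criteria are how the endpoint is assessed, and none of them tells an abstractor to fail a jargon-free but conflicting basal order.

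A reader might also fault the endpoint for passing control orders with no titration text. That is not an error under this protocol. Requiring such text would build the difference between the arms into the outcome, because only the DOS arm receives it by protocol.

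**Conclusion.** The point holds for the basal endpoint. The written rule falls short of the aim it serves: clarity is promised, the parallel prandial list scores it, and the basal list does not. An unclear or conflicting basal order without jargon is counted as a success.

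The size is unknown. It is tempting to take 100% − 54% = 46% from Study 3 as the share of control orders that could be mis-scored, and to build a power figure on it. Neither is supported. The 46% includes jargon failures already scored and comes from a different, mostly pre-EMR sample, and any rate for the DOS arm would be invented.

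Reading conflict as the main failure after the EMR is a fair inference from an incomplete sentence and the title of Figure 1, but no frequency is stated. The finding does not need it, because the omission is visible from the two lists alone.

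A reader might also object that the follow-up plan has no endpoint of its own. H.2.b already counts visits with primary care or endocrinology within 2 and 6 weeks, so a documentation endpoint would be an optional addition and not the repair of a defect.

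The consequence is confined to an unpowered secondary endpoint and to claims about discharge processes. The primary endpoint and the sample size stand.

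**What to change.** In H.2.b, add to the basal criteria: clear dosing instructions, including any titration text that is present. Do not require titration text.

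For both lists, state that clear includes no conflict within the prescription or with the consult notes. This matches the way Study 3 classified unclear instructions and settles the undefined term in the prandial list.

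Make the change before discharge orders are abstracted, so that both arms are scored by one rule. If abstraction has begun, re-score the orders already reviewed.

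The cost is a line of text in the endpoint definitions, one or two extra fields on the abstraction form and a little more abstraction time. The sample size, visits and primary analysis do not change.
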